9.7. Assessments at time of Disease Progression

If disease progression is suspected, investigations should be carried out as per local protocols. If progression is confirmed, a disease progression urgent event form must be submitted within 72 hours of becoming aware (see section 12.5.2 for more information).

Samples for translational research

• If a repeat biopsy is performed at the time of relapse, the block should be sent to the central laboratory (HMDS) (see section 10.1 and Laboratory Manual for details)

9.8. Follow up Assessments after Disease Progression

Following disease progression, patients will be seen annually. The following investigations will be performed:

- Remission status assessment (investigations as per local protocols)
- Assessment for late toxicity of nivolumab

N.B. confirmed disease progressions must be reported as urgent events within 72 hours of becoming aware (see section 12.5 (Urgent Events))

10. EXPLORATORY BIOLOGICAL STUDIES

Biological studies are an integral part of the trial and as such are not optional but will be built into the main study consent (apart from an optional biopsy of residual PET avid lesions). We will be collecting two types of sample: formalin fixed paraffin embedded tissue and blood.

There are two three central laboratories for the trial. The Haematological Malignancy Diagnostic Service (HMDS) in Leeds will be responsible for central pathology review using immunohistochemistry (IHC), gene expression profiling (GEP) and fluorescent in situ hybridisation (FISH) studies. The Weatherall Institute of Molecular Medicine, Oxford will be carrying out biomarker studies on blood samples using flow cytometry. The MRC-University of Glasgow Centre for Virus Research will perform TARC analysis on blood samples.

Sites must keep a record of all samples sent to central laboratories for the trial, and ensure they update the sample tracking website when samples are sent. —See the Laboratory Manual for more details of how to track samples.

10.1. Formalin fixed paraffin embedded blocks

Formalin fixed paraffin embedded (FFPE) tissue will be sent to HMDS, Leeds from the referring hospitals. This will preferably be from a lymph node biopsy taken at first relapse. In the absence of this material, the initial diagnostic sample will be acceptable. It should preferably be a biopsy from an involved lymph node, or solid tumour mass. In the absence of this, any diagnostic material is acceptable (e.g. bone marrow trephine biopsy with involvement by Hodgkin). The block should be sent to HMDS, Leeds. See the Laboratory Manual for details of how to send and log FFPE samples. The consent for laboratory studies will either accompany the tissue sample or a copy of the consent form will be faxed to HMDS. Laboratory processing of any samples will not occur until patient consent has been confirmed.

In addition, an optional biopsy will be performed of any PET avid residuum after nivolumab treatment. This will also be formalin fixed and paraffin embedded and sent to HMDS, Leeds.

If, following trial treatment, a biopsy is taken to confirm disease progression, the block should be sent to HMDS, Leeds.

 $3\mu m$ sections of the tissue block will be taken and immunohistochemistry performed. A panel of markers will be assessed for each case including: CD30, IRF-4, PAX-5, CD20, CD3, OCT-2, BCL-6, CD79, CD15 and LMP-1. Immunostaining for PD1, PD-L1 and PD-L2 will also be performed in most cases.

Sections of the block will also be prepared for FISH studies. The FISH studies conducted will include those for 9p24 abnormalities as these have previously been reported to be highly predictive of outcome (Roemer et al 2016). Probes will include CD274/PD-L1, PDCD1LG2/PD-L2, CEP9 and REL. Fifty Reed-Sternberg cells per slide will be reviewed and the FISH signals defined as disomic, polysomic, relative copy gain or amplified.

GEP will be performed using either or both of the HTG Immunopanel and the Affymetrix Human Transcriptome Array, which is a whole transcriptome array. These are two gene expression platforms currently being used in HMDS with bioinformatic support from within HMDS and in collaboration with the University of Leeds.

Once analysis is complete, blocks can be returned to sites at their request.

10.2. Peripheral blood samples

Research peripheral blood samples will also be collected as follows:

Timepoint	Sample required
Within 3 days prior to start of cycle 1	50ml peripheral blood in EDTA
	5ml peripheral blood in serum gel tube
Within 3 days prior to start of cycle 2	20ml peripheral blood in EDTA
	5ml peripheral blood in serum gel tube
Within 3 days prior to start of cycle 4	20ml peripheral blood in EDTA
	5ml peripheral blood in serum gel tube
Within 3 days prior to start of cycle 6	20ml peripheral blood in EDTA
	5ml peripheral blood in serum gel tube
Within 3 days prior to start of cycle 8	20ml peripheral blood in EDTA
	5ml peripheral blood in serum gel tube
1 month post treatment follow up visit	20ml peripheral blood in EDTA
	5ml peripheral blood in serum gel tube

Samples should be sent by first class mail to the central laboratory at the Weatherall Institute of Molecular Medicine, Oxford. No processing of the sample is required at site prior to sending. Samples taken on a Friday should be refrigerated over the weekend and sent on the next working day. Please refer to the Laboratory Manual for more details of how to send and log blood samples.

EDTA samples will be analysed at the Weatherall Institute of Molecular Medicine, Oxford. Immunophenotyping by multicolour flow panels and/or CyTOF (depending on cell recovery) will be performed on the blood to identify immune signatures prior to, during, and after nivolumab treatment. This may give important predictive and pharmcodynamic information. Panels for myeloid and T cell markers will be used. For patients with circulating activated T cells, these will be sorted and analysed functionally. Sequencing of TCR will also be performed. Any leftover material will be stored in a biobank for future use in ethically approved research, subject to patient consent.

Serum samples will be processed by the Weatherall Institute and frozen in the first instance. They will then be transferred to the MRC-University of Glasgow Centre for Virus Research where measurement of TARC (CCL17) levels will be performed. It is anticipated that samples will be transferred in one batch once all patients have completed trial treatment, and all TARC analysis will be performed retrospectively. Any leftover material following this analysis will be stored in a biobank for future use in ethically approved research, subject to patient consent.

Peripheral blood samples, or any products produced from these, will not be returned to sites.

10.3. Agreements and accreditations

The trial consent form will include provision for samples to be sent to, and stored at, the HMDS, and the Weatherall Institute of Molecular Medicine, Oxford and the MRC-University of Glasgow Centre for Virus Research. The ethical approval of the trial will cover storage and processing of

ANIMATE

samples at the HMDS₁-and the Weatherall Institute of Molecular Medicine, Oxford and the MRC-University of Glasgow Centre for Virus Research in accordance with the protocol.

HMDS is a CPA accredited laboratory with UKAS accreditation to ISO15189 standards.

UCL CTC will hold laboratory agreements with the HMDS, and the Weatherall Institute of Molecular Medicine, Oxford and the MRC-University of Glasgow Centre for Virus Research.

11. DATA MANAGEMENT AND DATA HANDLING GUIDELINES

Data will be collected from sites on version controlled case report forms (CRFs) designed for the trial and supplied by UCL CTC. Data must be accurately transcribed onto trial CRFs and must be verifiable from source data at site. Examples of source documents are hospital records which include patient's notes, laboratory and other clinical reports etc.

Where copies of supporting source documentation (e.g. autopsy reports, pathology reports, CT scan images etc.) are being submitted to UCL CTC, the patient's trial number must be clearly indicated on all material and any patient identifiers removed/blacked out prior to sending to maintain confidentiality.

Please note that, for this trial, patients must consent to their NHS/CHI being supplied to UCL CTC. This is required in order to allow for follow up via national registries where needed.

11.1. Completing Case Report Forms

All CRFs must be completed and signed by staff who are listed on the site staff delegation log and authorised by the PI to perform this duty. The PI is responsible for the accuracy of all data reported in the CRF.

All entries must be clear, legible and written in ball point pen. Any corrections made to a CRF at site must be made by drawing a single line through the incorrect item ensuring that the previous entry is not obscured. Each correction must be dated and initialed. Correction fluid must not be used.

The use of abbreviations and acronyms should be avoided.

11.2. Missing Data

To avoid the need for unnecessary data queries CRFs must be checked at site to ensure there are no blank fields before sending to UCL CTC (unless it is specifically stated that a field may be left blank). When data are unavailable because a measure has not been taken or test not performed, enter "ND" for not done. If an item was not required at the particular time the form relates to, enter "NA" for not applicable. When data are unknown enter the value "NK" (only use if every effort has been made to obtain the data).

11.3. Timelines for Data Return

CRFs must be completed at site and returned to UCL CTC as soon as possible after the relevant visit and within the following timeframes:

- Registration CRF to be faxed/emailed to UCL CTC in real time
- Post salvage CRF to be faxed/emailed to UCL CTC in real time
- Treatment CRFs to be sent to UCL CTC within 2 weeks of the end of each cycle
- Treatment Summary CRF to be sent to UCL CTC within 2 weeks of the decision to stop treatment (with the Treatment CRF for the last cycle given)
- Follow up CRFs to be sent to UCL CTC within 4 weeks of the patient being seen
- SAE forms to be faxed or emailed to UCL CTC within 24 hours of becoming aware of the event

- Pregnancy report forms to be faxed or emailed to UCL CTC within 24 hours of becoming aware of the pregnancy
- Post-allogeneic transplant urgent event form to be faxed or emailed to UCL CTC within 72 hours of becoming aware of the event
- Disease progression form to be faxed or emailed to UCL CTC within 72 hours of becoming aware of confirmed disease progression
- Death form to be faxed or emailed to UCL CTC within 24 hours of becoming aware of the death.
- New treatment form to be faxed or emailed to UCL CTC with the next due Follow up CRF.
- Transfer of care form to be faxed or emailed to UCL CTC within 2 weeks of the transfer of care to another site.
- Lost to follow up form to be faxed or emailed to UCL CTC within 1 month of becoming aware that the patient is lost to follow up.

Sites that persistently do not return data within the required timelines may be suspended from recruiting further patients into the trial by UCL CTC and subjected to a 'for cause' monitoring visit. See section 14.2 ('For Cause' On-Site Monitoring) for details.

11.4. Data Queries

Data arriving at UCL CTC will be checked for legibility, completeness, accuracy and consistency, including checks for missing or unusual values. Data Clarification Requests will be sent to the data contact at site. Further guidance on how data contacts should respond to data queries can be found on the Data Clarification Request forms.

12. PHARMACOVIGILANCE

12.1. Definitions

The following definitions have been adapted from Directive 2001/20/EC, ICH E2A "Clinical Safety Data Management: Definitions and Standards for Expedited Reporting" and ICH GCP E6.

Adverse Event (AE)

Any untoward medical occurrence in a patient treated on a trial protocol, which does not necessarily have a causal relationship with a trial treatment. An AE can therefore be any unfavourable and unintended sign (including an abnormal laboratory finding), symptom or disease temporally associated with the use of a trial treatment, whether or not related to that trial treatment. See section 12.2.1 for AE reporting procedures.

Adverse Reaction (AR)

All untoward and unintended responses to a trial treatment related to any dose administered. A causal relationship between a trial treatment and an adverse event is at least a reasonable possibility, i.e. the relationship cannot be ruled out.

Serious Adverse Event (SAE) or Serious Adverse Reaction (SAR)

An adverse event or adverse reaction that at any dose:

- Results in death
- Is life threatening (the term "life-threatening" refers to an event in which the patient was at risk of death at the time of the event. It does not refer to an event that hypothetically might have caused death if it were more severe)
- Requires in-patient hospitalisation or prolongs existing hospitalisation
- Results in persistent or significant disability/incapacity
- Is a congenital anomaly or birth defect
- Is otherwise medically significant (e.g. important medical events that may not be immediately life-threatening or result in death or hospitalisation but may jeopardise the patient or may require intervention to prevent one of the other outcomes listed above)

See section 12.2.2 for SAE reporting procedures.

Suspected Unexpected Serious Adverse Reaction (SUSAR)

An adverse event meeting the following criteria:

- Serious meets one or more of the serious criteria above
- Related assessed by the local investigator or sponsor as causally related to one or more elements of the trial treatment
- Unexpected the event is not consistent with the applicable reference safety information (RSI)

See section 12.3 for reporting procedures for these events.

Adverse event of special interest (AESI)

An AE that is of particular interest to the Trial Management Group, even if it occurs outside the standard AE reporting timeframes for the trial. They are to be reported on an SAE form, regardless of their seriousness. The AEs of special interest for this trial are:

AESIs to be reported as SAEs

- Autoimmune diarrhoea / colitis
- Autoimmune pneumonitis
- Autoimmune hepatitis
- Autoimmune dermatitis
- Immune related endocrinopathies
- Autoimmune renal toxicity
- Autoimmune neurological toxicity
- Autoimmune uveitis
- Potential drug induced liver injury (pDILI)
- Overdoses (regardless of whether patient experiences any adverse events as a result)
- Grade 3 or 4 infusion reactions to nivolumab

See section 12.4 for reporting procedures for these events.

Urgent event

Urgent events for this trial are:

- Grade 3/4 graft versus host disease (patients who have allogeneic transplant only)
- Hyperacute graft versus host disease (patients who have allogeneic transplant only)
- Steroid-responsive febrile syndrome (patients who have allogeneic transplant only)
- Disease progression
- Death

See section 12.5 for reporting procedures for these events.

Overdose, trial treatment error, or occupational exposure

Refer to section \Box for details on reporting of these events. Additionally refer to section 12.4.3 for details of reporting overdoses.

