8.5. Management of Adverse Events

8.5.1. Autoimmune complications

Because of its mechanism of action, autoimmune complications are common with nivolumab. Where sites have local policies for management of autoimmune toxicity, these may be followed. Where there is no local policy, suggested guidelines for management of such autoimmune complications are set out below. Clinicians are also advised to refer to the manufacturer's guidelines (see summary of product characteristics).

Autoimmune toxicities are regarded as AEs of special interest for this trial, requiring expedited reporting to UCL CTC. Please refer to section 12.4 for details of how and when to report autoimmune events.

If treatment is delayed by >4 weeks due to autoimmune toxicity, the subject should be permanently discontinued from study treatment.

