8.5.1.8 Management of other immune-related adverse reactions

Adequate evaluation should be performed to confirm aetiology and exclude other causes.

See summary of product characteristics for detailed guidance on management of individual toxicities.

CTCAE v5 grade	Action – trial treatment	Recommended management of toxicity
Grade 1	Continue nivolumab treatment at 240mg.	Treatment for symptoms as per local policy.
Grade 2 (first occurrence)	Delay nivolumab treatment Restart nivolumab at 240mg if/when returns to ≤G1. If steroids given, patient must have been weaned to ≤10mg per day (or equivalent) before restarting treatment. Maximum permitted delay 4 weeks.	Treat symptoms as per local guidelines. Steroid treatment as per local policy; taper prior to restarting nivolumab.
Grade 3 (first occurrence – except myocarditis – see below)	Delay nivolumab treatment. Restart nivolumab at 240mg if/when returns to ≤G1. If steroids given, patient must have been weaned to ≤10mg per	Treat symptoms as per local guidelines. Steroid treatment as per local policy; taper prior to restarting nivolumab.

	day (or equivalent) before restarting treatment.	
	Maximum permitted delay 4 weeks.	
Grade 3 myocarditis	Permanently discontinue nivolumab treatment.	Refer for specialist opinion. Manage as per local policy.
Grade 4 or recurrent grade 3;	Permanently discontinue	Treat symptoms as per local
Persistent grade 2 or 3 despite	nivolumab treatment.	guidelines.
intervention;		Steroid treatment as per local
Inability to reduce corticosteroid		policy.
dose to 10mg prednisolone per day or equivalent		Seek specialist opinion.

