9.4. Assessments during Treatment

During treatment the patient should be seen every 2 weeks and the following assessments performed within 3 days prior to the start of each cycle:

- Clinical examination
- Full blood count with differential
- Biochemistry (ALT/AST, total bilirubin, alkaline phosphatase, urea, creatinine, calcium, magnesium, sodium, potassium, LDH, albumin, urate, glucose)
- Tests for autoimmune conditions (amylase, lipase, ACTH)
- Cycles 3, 5 & 7: pregnancy test (urine or serum; WOCBP only)
- Cycle 4 and cycle 7: Thyroid function tests (TSH & Free T4; Free T3 to be performed if TSH/Free T4 abnormal)
- Adverse event assessment

The following investigations must be carried out on the day of nivolumab administration:

Oxygen saturation measured by pulse oximetry at rest

Blood samples for translational research

Blood samples are to be taken and sent to the central laboratory at the Weatherall Institute
of Molecular Medicine, Oxford within 3 days prior to the start of cycles 2, 4, 6 and 8, and
at the 1 month post-treatment visit (see section 10.2 and Laboratory Manual for more
details)

Scanning required after cycle 4

- PET-CT scan to be carried out on cycle 4, day 11-13 as per trial requirements on an approved scanner, and images sent to the PET core lab for central review (PET4; see trial Imaging Manual for details).
- Contrast enhanced CT scan (ceCT). If feasible, this should be performed at the same imaging session as the PET-CT. If performed at the same session, the ceCT scan should be performed after the low dose PET-CT (see trial Imaging Manual for details).

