12.4.1. Autoimmune events due to Nivolumab

The following adverse events of special interest for Nivolumab must be reported on the appropriate AE of Special Interest form within **24 hours of confirmed diagnosis.**

The following adverse events of special interest for Nivolumab must be reported on an SAE report form within **24 hours of confirmed diagnosis.** Please note that any signs and symptoms should be treated on their merits and reported as AEs/SAEs as applicable pending confirmation of diagnosis.

To summarise, the reporting requirements for **autoimmune events** based the treatment arm are as follows: (please note that the reporting window for autoimmune events differs to those for non-autoimmune SAEs; see section 12.2.2 for details).

Next Treatment	Reporting window for autoimmune toxicity
No treatment or further chemotherapy	From first administration of nivoumab until 5 months post last dose of trial treatment (or after this date if the investigator feels the event is related to nivolumab).
Autologous stem cell transplant	From first administration of nivoumab until 5 months post last dose of trial treatment (or after this date if the investigator feels the event is related to nivolumab).
Allogeneic stem cell transplant	From first administration of nivoumab until 5 months post last dose of trial treatment (or after this date if the investigator feels the event is related to nivolumab).
	Please note that colitis, dermatitis and hepatitis occurring after transplant day 0 should be reported as graft-versus-host disease in the first instance unless otherwise proven to be of autoimmune origin (see section 12.5 (Urgent Events) for details of reporting graft-versus-host disease).

Please note that confirmed autoimmune events must be reported to the CTC on an SAE report form even if the patient has received further treatment for their lymphoma within the 5 months after completing nivolumab.

Events will be collected as follows:

Event	Description See section 8.5 for detailed definitions	Form required	Timeframe
Autoimmune diarrhoea / colitis	Grade ≥2 diarrhoea persisting >48 hours and not suspected clinically or confirmed on lab testing to be due to infective causes	SAE report	Within 24 hours of confirmed diagnosis
Autoimmune uveitis	New or worsening inflammation of the eye, with ocular pain, erythema or blurring of vision.	SAE report	Within 24 hours of confirmed diagnosis

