18.2.2. Analysis of secondary endpoints and secondary analyses

Survival endpoints:

Progression free survival (PFS)

PFS time will be measured from the date of the PET scan after first or second line salvage treatment (PET0) until the date of progression or death (whichever comes first). Patients who are alive and progression free will be censored at the date last seen.

Overall survival (OS)

OS time will be measured from the date of the PET scan after first or second line salvage treatment (PET0) until the date of death. Patients who are alive will be censored at the date last seen.

Analysis of PFS and OS will take place once we have 1 year follow-up for all patients. Kaplan Meier survival analyses will be used for both.

Subgroup analyses will be performed for responders and non-responders i.e. do patients with a PMR do worse than those with a CMR after nivolumab treatment. Kaplan Meier survival analysis and Cox regression may be used, although this will be dependent on the numbers of patients with a response and the numbers of events.

PFS and OS will also be analysed by further treatment i.e. did the patient go on to have an allograft or autograft, though we acknowledge that numbers will be very small so analyses will be descriptive.

CMR/PMR rates

Proportions of patients achieving CMR and PMR will also be presented.

Adverse events:

Analysis will focus on grade 3/4 adverse events. The worst grade seen per patient will be shown for each event type.

AESIs will be reported in more detail, with autoimmune events of any grade presented. All analysis will be descriptive.

Transplant related mortality and the rate of serious complications of allo SCT will presented, though again, it is likely only descriptive statistics will be used.

Other analyses:

The association between pre-nivolumab biological parameters and response to nivolumab will be investigated. As numbers will be very small mostly descriptive statistics will be used i.e. numbers and percentages will be presented for binary/categorical data and means and medians (with ranges) for continuous measurements.

We will also look at changes in TARC levels in responders and non-responders.

PET negative patients not treated with nivolumab

We will look at PFS, OS and subsequent treatments for patients who are PET negative following first or second line salvage treatment (i.e. at PET0).

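### The closed AESI list leaves out other immune-related reactions and sets a floor for colitis, so the any-grade autoimmune table can miss events after the ordinary AE window closes

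*Protocol*

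**What the plan says.** Four parts of the protocol bear on which immune events are collected and for how long.

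- **General rule.** Section 8.5.1: "Autoimmune toxicities are regarded as AEs of special interest for this trial, requiring expedited reporting to UCL CTC". No organ or grade limit is attached. Within it, section 8.5.1.8, "Management of other immune-related adverse reactions", runs from grade 1 to grade 4 and names myocarditis.
- **The list.** Section 12.1 introduces its list with "They are to be reported on an SAE form, regardless of their seriousness. The AEs of special interest for this trial are". It gives eight autoimmune classes: diarrhoea/colitis, pneumonitis, hepatitis, dermatitis, endocrinopathies, renal, neurological and uveitis. It adds potential drug-induced liver injury, overdose and grade 3-4 infusion reactions. Section 12.2.2 repeats the same eleven items, and the table in 12.4.1 describes the same eight autoimmune classes. None has a residual class.
- **The colitis entry.** In 12.4.1 it begins "Grade ≥2 diarrhoea persisting >48 hours and not suspected clinically".
- **The analysis.** Section 18.2.2 says that adverse event analysis will centre on grades 3 and 4, but "AESIs will be reported in more detail, with autoimmune events of any grade presented".

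Section 3.2 makes safety a secondary endpoint and singles out autoimmune toxicity.

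**The concern.** An event such as myocarditis is an AESI under 8.5.1 but not under 12.1. The same holds for anything else handled under 8.5.1.8. Immune-mediated diarrhoea of grade 1 has its own row in 8.5.1.1 but falls below the threshold in 12.4.1.

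The classification matters because AESI status decides how long an event is collected. The protocol gives autoimmune AESIs a longer window than ordinary AEs and keeps that window open through later lymphoma treatment. Section 12.2.2 explains that the separate AESI rules exist so that important immune-related reactions go on being reported after a new treatment starts. A list narrower than the rule in 8.5.1 works against that purpose for the classes it leaves out. An analysis plan cannot restore events that were never collected.

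**Working it through.** The plan states no figure on this point, so the check sets the passages side by side.

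**1. Two windows.**
- Ordinary AEs (12.2.1): from the start of nivolumab to 3 months after the last dose or the start of the next lymphoma treatment, whichever comes first.
- Autoimmune AESIs (12.4.1): from first dose to 5 months after the last dose, whether or not further lymphoma treatment has begun, and later if the investigator judges the event related.

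Let t be the months from last dose to next lymphoma treatment. The stretch covered by the AESI window but not the AE window is 5 − min(3, t) months. With no new treatment by 3 months it is 5 − 3 = 2 months. With new treatment earlier it is longer; for illustration, t = 1 gives 5 − 1 = 4 months. Section 12.2.1 itself expects most patients to have moved on to further lymphoma treatment by 3 months, so the longer gap is the usual case.

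**2. Inside the AE window.** All adverse events of any grade are recorded on the CRF. Myocarditis and grade 1 diarrhoea are therefore collected here. The protocol asks only whether an ordinary AE is related to treatment (12.2), not whether it is immune-mediated.

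**3. After the AE window, up to 5 months.**
- *Listed autoimmune class:* SAE form within 24 hours of confirmed diagnosis, whatever the seriousness.
- *Unlisted immune event, non-serious:* neither the AE rule nor the AESI rule requires a report.
- *Unlisted immune event, serious, no new treatment yet:* reportable as an SAE to 5 months (12.2.2).
- *Unlisted immune event, serious, after new treatment:* the opening sentence of 12.2.2 still requires a report if the investigator thinks it related. The exemption list in the same section exempts events after further lymphoma treatment unless they are autoimmune events classed as AESIs. The two statements disagree for exactly these events.

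**4. The colitis entry.** The other seven autoimmune descriptions in 12.4.1 carry no grade floor; this one does. The table header refers to section 8.5 for detailed definitions. There, 8.5.1.1 has a grade 1 row and describes colitis by abdominal pain or blood in the stool. Grade 1 immune diarrhoea is thus excluded by the description. Colitis with pain or blood but few stools is left unclear: outside the description, but arguably inside by the cross-reference.

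**5. The analysis.** The any-grade presentation in 18.2.2 stands in the sentence on AESIs, while the general AE analysis is directed at grades 3 and 4. If the autoimmune table follows the AESI reports, it inherits the list's gaps.

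**The case against.** The strongest reply is that several other routes collect these events. All AEs are recorded during the AE window. Serious events have a 5-month window while no new treatment has started, and a related event can be reported later. Section 12.2.2 says that events exempt from an SAE form must still go on the CRF. Late nivolumab toxicity is assessed at months 6, 9 and 12 and then yearly (9.6.2), and yearly after progression (9.8). The AESI list is by definition what the Trial Management Group chooses to watch. A grade and duration floor on a non-specific symptom is a defensible choice for expedited reporting. The analysis is descriptive, and the protocol does not say that the table uses SAE forms alone.

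Much of this stands. A reader might infer that whole classes of event are lost and that the autoimmune rate is understated by some number of points. The documents do not support that: the events are recorded within the AE window, and no rate is given for those outside it. What remains is that the CRF rule for exempt events sits beside an earlier AE cut-off in 12.2.1, and that the late-toxicity visits begin after the 5-month window, with no grading or immune attribution described.

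Two further inferences should be resisted. Pancreatitis might be read as another omitted AESI, because of "Tests for autoimmune conditions (amylase, lipase, ACTH" in 9.4 and its mention in section 2.1 among grade 3-4 events of an earlier nivolumab study. Section 8.5.1 never names it as an autoimmune complication, so this is inference only. The rule after an allograft, that "colitis, dermatitis and hepatitis occurring after transplant day 0 should be reported as graft-versus-host disease in the first instance", might look like a further loss. The same sentence excepts events proven to be autoimmune, which remain AESIs, and non-hyperacute graft-versus-host disease of grade 1-2 is not a trial endpoint.

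**Conclusion.** The contradiction is real and confined to reporting. Section 8.5.1 and the closed lists disagree on whether other immune-related reactions, including myocarditis, are AESIs. The colitis threshold in 12.4.1 does not match the any-grade presentation in 18.2.2. The consequence is a risk of omission, not a demonstrated under-count. It falls mainly on non-serious unlisted events and low-grade colitis occurring after the AE window closes, and on serious unlisted events after new treatment, where 12.2.2 is inconsistent. The gap lasts at least 2 months per patient before the 5-month window ends, and longer for those treated sooner. The number of events in it cannot be derived from the documents. The conclusion assumes that sites follow the lists and windows as written. The point is worth correcting because autoimmune toxicity is singled out in the safety endpoint and the correction is small.

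**What to change.** In sections 12.1, 12.2.2 and 12.4.1, add an AESI class for any other immune-related adverse reaction as in 8.5.1.8, including myocarditis, with the same SAE form and the same 5-month window through later treatment. The exemption in 12.2.2 works through AESI status, so it would then cover these events without further change.

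In 12.4.1, align the diarrhoea/colitis description with 8.5.1.1 and with 18.2.2, so that confirmed immune-mediated diarrhoea or colitis of any grade is collected over the autoimmune window.

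A sentence saying that the autoimmune table also draws on ordinary AE records would help within the AE window but would not close the gap after it.

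The cost is protocol wording, matching form entries and a few more expedited forms. Treatment rules are untouched.
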